4.3 Participant Exclusion Criteria

Individuals meeting any of the following criteria will be excluded from study participation:

1. Has used an investigational drug agent or investigational device within 12 weeks of baseline. However, ARVs obtained through expanded access programs are permitted.
2. Has received prior therapy with an anti-PD-1, anti-PD-L1, or anti-PD-L2 agent.
3. Known allergy to any component of the pembrolizumab formulation.
4. Systemic steroid therapy or other immunosuppressive therapy in the 3 months prior to enrollment. (Inhaled or topical corticosteroids are permitted.)
5. Has used an immunotherapeutic agent (e.g., cyclosporine, tacrolimus, mycophenolate mofetil, azathioprine, sirolimus, therapies targeting tumor necrosis factor- α) within 6 months of baseline.
6. Has received any vaccine, live or inactivated, within 30 days of baseline, or plans to receive any vaccine within 16 weeks of receiving pembrolizumab.
7. Has active autoimmune disease or a history of autoimmune disease that has required systemic treatment (e.g., with use of disease-modifying agents,

corticosteroids, or immunosuppressive drugs). Such autoimmune diseases include for example psoriasis, systemic lupus erythematosus, autoimmune uveitis, autoimmune hepatitis, inflammatory colitis, rheumatoid arthritis, Guillain-Barré syndrome, Stevens-Johnson syndrome, or toxic epidermal necrolysis. Replacement therapy (e.g., T4) is not considered a form of systemic treatment.

8. Has known history of, or any evidence of active, non-infectious pneumonitis.
9. Malignancy requiring systemic therapy, or a history of malignancy that required systemic therapy within the past 5 years. However, cutaneous basal cell carcinoma or cutaneous Kaposi sarcoma not requiring systemic therapy will not be exclusionary.
10. Has known active hepatitis B (HBV) or potential for HBV reactivation (e.g., hepatitis B surface antigen [HBS] reactive, HBV DNA positive, or isolated anti-core antibody positive; individuals who are anti-HBS antibody positive with or without anti-core Ab are eligible).
11. Has known active hepatitis C (HCV; e.g., HCV RNA [qualitative] is detected). Patients who have sustained virologic response (SVR) to anti-HCV treatment are eligible if at least 24 weeks have passed since achieving SVR.
12. Females who are pregnant, planning to become pregnant, or are breastfeeding.
13. Has known psychiatric or substance abuse disorders that would interfere with cooperation with the requirements of the study.
14. History or other clinical evidence of:
 - a. Significant or unstable cardiac disease (e.g., angina, congestive heart failure, myocardial infarction).
 - b. Significant pulmonary disease (e.g., chronic obstructive pulmonary disease, asthma requiring systemic therapy).
 - c. Severe illness, chronic liver disease, malignancy, immunodeficiency other than HIV, active systemic infection (other than HIV) requiring therapy.
15. Opportunistic infection requiring maintenance therapy, including toxoplasmosis, fungal infections other than candida (e.g., cryptococcosis, histoplasmosis, coccidioidomycosis), atypical mycobacterial infection. Secondary *Pneumocystis*, candida, varicella-zoster virus (VZV), and herpes simplex virus (HSV) prophylaxis will be permitted.
16. Active or history of tuberculosis (TB), or positive TB QuantiFERON Gold test.
17. Known osteoporosis or diabetes mellitus.
18. Hemoglobin A1c > 6%.
19. Fasting triglyceride > 300 mg/dL.
20. Any condition that, in the opinion of the investigator, would make the participant unsuitable for the study.

Co-enrollment guidelines: Co-enrollment in other trials is restricted, other than enrollment on observational studies or expanded access studies for antiretroviral agents, during the first 48 weeks of the study. If NIH blood volume limits are exceeded due to the requirements of the combined studies, then co-enrollment will not be permitted.

4.4 Justification for Exclusion of Special Populations

Females who are pregnant or of reproductive potential: Dedicated developmental and fetal toxicity studies of pembrolizumab have not been conducted in humans or animals. However, animal models of the PD-1/PD-L1 pathway suggest that perturbations may affect the maternal immune response to fetal tissue. Human IgG4 antibodies (the IgG subtype of pembrolizumab) are also known to cross the placental barrier and be transmitted from mother to fetus. Additionally, pregnancy may affect the participant's immune response. Therefore, pregnant participants are excluded from this study. Per recommendations in the pembrolizumab package insert, contraception (for this study, two forms, one of which must be a barrier-based method, see Section 4.2) will be required from 30 days prior through 120 days after the pembrolizumab dose.

Breastfeeding: It is unknown whether pembrolizumab is excreted in human milk. Since many drugs are excreted in human milk, and because of the potential for serious adverse reactions (ARs) in the nursing infant, participants who are breast-feeding are not eligible for enrollment.

Exclusion of children: Because there are insufficient data regarding dosing or AEs available in adults to judge the potential risk in children, and because this is the first safety study in HIV-infected patients without cancer, children are excluded from this study.

5 Study Agent/Interventions

5.1 Disposition, Dispensation, and Accountability

Study agent or placebo will be distributed and accounted for by the NIH pharmacy according to standard pharmacy procedures.

5.2 Formulation, Packaging, and Labeling

Each pembrolizumab ready-for-injection vial will be further diluted according to the manufacturer's label instructions and administered as an IV infusion to the study subject. Each IV infusion bag for both study agent and placebo will be individually labeled with the subject ID number, administration instructions, and the Investigational

Use Statement (“Caution: New Drug-Limited by Federal [USA] Law to Investigational Use”).

5.3 Study Agent Storage and Stability

Vials of pembrolizumab injection solution should be stored at 2°C-8°C and should not be shaken or frozen. Vials should be kept in their cartons and protected from light. Diluted study drug may be stored at 2°C-8°C for up to 24 hours, or room temperature (approximately 22°C) for up to 6 hours.

5.4 Preparation, Administration, and Dosage of Study Agents

Pembrolizumab is provided as a ready-for-injection solution at 100 mg/4 mL and should be further diluted for administration.

Participants will receive a single 200-mg dose of pembrolizumab in 5% dextrose or placebo (matching diluent). To maintain the double-blind, pembrolizumab and placebo infusions should be prepared in matching diluent solutions and administered in the same manner (please see administration instructions below).

Preparation: When preparing pembrolizumab, allow the required number of vials to equilibrate to room temperature. For IV infusion, the study drug should be diluted to a final concentration between 1 and 10 mg/mL in 5% dextrose solution for injection, USP. The placebo will be an equivalent volume of 5% dextrose solution for injection, USP.

In the event of a diluent shortage, 0.9% sodium chloride solution may be used in place of 5% dextrose to prepare pembrolizumab and placebo infusions.

Administration: Pembrolizumab and placebo infusion should be administered over 30 minutes through an IV line containing a sterile, non-pyrogenic, low-protein-binding 0.2-5- μ m in-line or add-on filter. Pembrolizumab should not be co-administered with other drugs in the same infusion line.

5.5 Randomization and Blinding

Eligible participants will be allocated 3:1 to study agent or placebo. A randomization scheme will be generated by the study statistician who will provide a randomized list of arm assignments to the NIH CC Pharmacy. Block randomization will be designed to ensure that some participants among the first 5 enrolled will receive pembrolizumab.

Study participants and the study team will be blinded through week 16 of the last participant treated.

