3.1 Description of the Study Design

Twenty adults (≥ 18 years) with HIV infection will be enrolled. Eligible participants will be INRs, with a recent CD4+ T-cell count >100 cells/mm³ and ≤ 350 cells/mm³, who have been on a cART regimen for at least 12 months and on a stable regimen for at least 4 weeks and have evidence of viral suppression.

Participants will be randomized 3:1 to receive either a single 200-mg dose of pembrolizumab or placebo via IV infusion at baseline. The dosage is based on the recommendation of Merck investigators and is the dose currently recommended on their product label. Inclusion of a placebo group will allow a blinded assessment of adverse events (AEs) and provide a control group with which to compare PD-1 expression levels over time. Participants will return for follow-up visits at weeks 1, 2, 3, 4, 6, 9, 12, 16, 24, 36, and 48, and will have phone calls with the study team at weeks 60, 72, 84, and 96. Blood will be collected at every visit for clinical and research evaluations. Participants will undergo leukapheresis at screening (after confirmation of eligibility) with optional leukapheresis at week 3 or 4 and week 12.

Five participants will be enrolled initially and followed for 90 days for safety outcomes. No additional participants will be enrolled until the DSMB has reviewed the 90-day safety data and recommended that the protocol can resume enrollment.

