3.2 Study Endpoints

3.2.1 Primary Endpoint

Frequency of either Grade 3 or higher AEs or Grade 2 or higher autoimmune events requiring corticosteroid therapy that are possibly, probably, or definitely related to pembrolizumab.

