5.5.1 Emergency Unblinding

If a participant experiences an AE whose management (e.g., diagnostic procedures, treatment) in the opinion of the principal investigator (PI) or designee would differ depending on the study arm, or in the case of pregnancy of a participant's partner, then the PI or designee will contact the NIH CC Pharmacy for release of the randomization code. The sponsor and data and safety monitoring board (DSMB) executive secretary will be informed within 1 business day of any request for unblinding. The participant will remain enrolled in the study and the data will be used for analysis.

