5.8 Management of Study Drug-related AEs

In the event of AEs related to the study drug, participants will receive appropriate supportive care measures as deemed necessary by the treating investigator. Given that management may depend on knowledge of the underlying treatment arm, as noted above, the PI or designee may unblind (see emergency procedure for unblinding) to ensure that the diagnostic evaluations and therapeutic interventions are directed appropriately. Suggested supportive care measures for the management of pembrolizumab-related AEs with potential immunologic etiology are outlined in Appendix A. Where appropriate, these guidelines include the use of oral or IV treatment with corticosteroids as well as additional anti-inflammatory agents if symptoms do not improve with administration of corticosteroids. Note that several courses of steroid tapering may be necessary as symptoms may worsen when the steroid dose is decreased. For each disorder, attempts should be made to rule out other causes such as bacterial or viral infection, which might require additional supportive care. The treatment guidelines are intended to be applied when the investigator determines the events to be related to pembrolizumab.

Note: if after the evaluation, the event is determined not to be related, the investigator does not need to follow the treatment guidance (as outlined in Appendix A).

It may be necessary to perform conditional procedures such as bronchoscopy, endoscopy, or skin photography as part of standard clinical evaluation of the event.

6 Study Schedule

NOTE: Five participants will be enrolled initially and followed for 90 days for safety outcomes. No additional participants will be enrolled until the DSMB has reviewed the 90-day safety data and recommended that the protocol can resume enrollment.

All study visits will be done at the NIH CC. A table of the study schedule is presented in [Appendix B](#).

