12.1 Documenting, Recording, and Reporting Adverse Events

All AEs occurring from the time of the initial leukapheresis through week 48 will be documented, recorded, and reported. If no leukapheresis is performed, then all AEs occurring from the time of pembrolizumab administration through week 48 will be documented, recorded, and reported. Between weeks 48 and 96, reporting will be limited to only those SAEs and autoimmune events that are possibly, probably, or definitely related to pembrolizumab.

At each contact with the participant, information regarding AEs will be elicited by appropriate questioning and examinations and will be:

- documented in the participant's medical record/source document,
- recorded in CRIMSON, and
- reported as outlined below (e.g., IND sponsor and FDA).

If a diagnosis is clinically evident (or subsequently determined), then the diagnosis rather than the individual signs and symptoms or lab abnormalities will be recorded as the AE.

All abnormal laboratory findings will be reviewed on a routine basis by the PI to identify potential safety signals. An abnormal lab not included on the toxicity table should be assessed in a similar fashion to the criteria above.

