12.2.2 Causality

Causality (likelihood that the event is caused by the study agent) will be assessed considering the factors listed under the following categories:

Definitely Related

- reasonable temporal relationship
- follows a known response pattern
- clear evidence to suggest a causal relationship
- there is no alternative etiology

Probably Related

- reasonable temporal relationship
- follows a suspected response pattern (based on similar agents)
- no evidence of a more likely alternative etiology

Possibly Related

- reasonable temporal relationship
- little evidence for a more likely alternative etiology

Unlikely Related

- does not have a reasonable temporal relationship
OR
- good evidence for a more likely alternative etiology

Not Related

- does not have a temporal relationship
OR
- definitely due to an alternative etiology

Note: Other factors should also be considered for each causality category when appropriate. Causality assessment is based on available information at the time of the assessment of the AE. The investigator may revise the causality assessment as additional information becomes available.

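### The relatedness judgement in the primary endpoint can be made or changed with the arm known: mainly through individual code release with no prior causality record, and to a smaller extent through study-wide unblinding before all-AE collection ends

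*Combined protocol and SAP*

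**What the plan says.** **Endpoint.** Section 3.2.1 counts Grade 3 or higher AEs and Grade 2 or higher "autoimmune events requiring corticosteroid therapy that are possibly, probably, or definitely related to pembrolizumab". Section 14 describes the primary safety outcome by the same grades and steroid requirement, but with no relatedness condition. Neither section gives a time window.

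**Purpose of placebo.** Section 3.1: "Inclusion of a placebo group will allow a blinded assessment of adverse events (AEs".

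**Individual unblinding.** Section 5.5.1 has the code released for an AE "whose management (e.g., diagnostic procedures, treatment) in the opinion of the principal investigator (PI) or designee would differ depending on the study arm". The sponsor and the DSMB executive secretary are told within 1 business day, and the participant's data stay in the analysis. Section 5.8 also permits unblinding to direct work-up and treatment.

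**Causality.** The investigator judges it (12.2). Section 12.2.2 adds: "The investigator may revise the causality assessment as additional information becomes available".

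**Study-wide unblinding.** Section 5.5: "Study participants and the study team will be blinded through week 16 of the last participant treated".

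**Collection.** Section 12.1: "All AEs occurring from the time of the initial leukapheresis through week 48 will be documented, recorded, and reported". For weeks 48-96, "reporting will be limited to only those SAEs and autoimmune events that are possibly, probably, or definitely related to pembrolizumab". Section 12.3.2.1 requires all serious AEs (SAEs) to be reported whatever their relationship, and narrows to related ones only after week 96.

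**The concern.** Under 12.2.2, a rating of possibly related needs only plausible timing and little evidence for a likelier cause. That is a low and subjective threshold, so knowing the arm can change the answer. On pembrolizumab it can tip an uncertain event towards related. On placebo, an event cannot logically be attributed to a drug the participant did not receive.

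Individual release matters most. Its trigger selects events whose treatment depends on arm, and autoimmune events that may need corticosteroids are natural candidates. Section 5.8 applies the Appendix A guidance, which includes corticosteroids, when the investigator judges the event related to pembrolizumab. Knowing the arm can therefore touch two parts of the endpoint: relatedness and the steroid requirement. Telling the sponsor and the DSMB records that unblinding happened. It does not preserve what the investigator thought beforehand.

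At stake are the AE probability among 15 pembrolizumab recipients, on which Section 14 concentrates, and the use of placebo events to temper concern.

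**Working it through.** **1. The plan's own figures.** Table 3 is 1 - (1 - p)^15. At p = 0.15 this gives 0.913, as stated, and the other five columns also reproduce. Fisher's exact test for 0/5 against 9/15 gives p = 0.038, and against 8/15 gives p = 0.055, so the stated threshold of 9 is right. No figure in the plan is in error; the issue is possible bias.

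**2. Individual release.** Set side by side, 5.5.1 and 5.8 permit release, 12.2 assigns the judgement to the investigator, and 12.2.2 permits revision. None asks for a record before release or marks a judgement made after it. The documents give no rate of emergency unblinding, so its size cannot be computed.

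**3. Study-wide unblinding.** Inputs: 20 participants (3.1), 2-year accrual taken as 104 weeks (Protocol Summary), code open 16 weeks after the last dose (5.5), all AEs to week 48 (12.1). Assumption: even dosing, without or with a 13-week hold after participant 5 (the 90-day review), total length fixed.

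Participant i, dosed at t_i, is blinded for b_i = t_20 + 16 - t_i weeks. Open time before week 48 is max(0, 48 - b_i).

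- No hold: spacing 104/19 = 5.47 weeks. The last six participants have 32.0, 26.5, 21.1, 15.6, 10.1 and 4.6 open weeks, a sum of 109.9. Share: 109.9/(20 x 48) = 11.4%.
- Hold: spacing (104 - 13)/19 = 4.79 weeks. The last seven have 32.0, 27.2, 22.4, 17.6, 12.8, 8.1 and 3.3, a sum of 123.4. Share: 123.4/960 = 12.9%.
- Months 1-5, the typical onset period in 8.1 (weeks 4.35 to 21.74 at 4.348 weeks per month; 17.39 x 20 = 347.8 participant-weeks): open time is 5.74 + 0.27 = 6.01 weeks without the hold (1.7%) and 5.74 + 0.95 = 6.69 with it (1.9%).

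| | 104-week accrual (no hold / hold) | 52-week accrual (no hold / hold) |
|---|---|---|
| Open at week 16 visit | 0 / 0 of 20 | 0 / 0 of 20 |
| Week 24 | 2 / 2 | 3 / 4 |
| Week 36 | 4 / 5 | 8 / 10 |
| Week 48 | 6 / 7 | 12 / 15 |
| Share of weeks 0-48 | 11.4% / 12.9% | 21.2% / 27.5% |
| Share of months 1-5 | 1.7% / 1.9% | 2.6% / 3.2% |

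The 52-week column is a stress case; the plan states 2 years. If the blind ran to the last participant's week 48 visit, every entry would be 0.

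**4. Sensitivity to one judgement.** Clopper-Pearson: 1/15 = 6.7% (95% CI 0.2% to 31.9%); 2/15 = 13.3% (1.7% to 40.5%). In Section 14's Fisher example, counting one placebo event moves p from 0.038 (0/5 against 9/15) to 0.30 (1/5 against 9/15).

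**The case against.** The study-wide route is small. The blind is tied to the last participant, so 13-14 of 20 stay blinded through their own week 48 under the stated accrual unless their code is released individually. At Section 14's 15% rate, 15 recipients give 15 x 0.15 = 2.25 expected events. If onset were uniform over weeks 0-48, about 0.26-0.29 of these would fall after unblinding; if all fell in months 1-5, about 0.04. This stands, and makes the route secondary. It does not remove it: 8.1 reports onset as late as 21 months, and the hypophysitis in the single-dose anti-PD-L1 study described in 1.1 appeared about 9 months after dosing.

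Emergency release is a necessary safety provision, and AEs are recorded at each contact (12.1). Section 5.8 starts from AEs already related to study drug, which implies some earlier judgement. All true, but no record of that judgement is required before release. The safety review and communications plan (12.7.1) was not supplied and might contain such a step.

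If Section 14's wording governs, attribution does not enter the primary outcome at all. Nothing says that it governs. Through week 48 the effect can be checked, because all AEs are recorded whatever their attribution. Section 14 also uses placebo mainly informally, which limits the harm to the between-arm comparison.

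A reader might infer that 12.3.2.3 conflicts with 12.1 because it lists immune-mediated AEs with no relatedness condition. It sets an expedited reporting channel and deadline and does not clearly contradict 12.1.

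**Conclusion.** The point holds as a gap in protecting a subjective endpoint component. The main route, individual code release, rests on the text alone and has no computable frequency. The secondary route covers about 11-13% of weeks 0-48 and under 2% of months 1-5, given even accrual over 2 years; faster accrual raises both. Separately, 3.2.1 and Section 14 define different counts, neither with a time window, and 12.1 and 12.3.2.1 disagree on SAE scope for weeks 48-96. Those are consistency matters and add no weight to the blinding point.

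Four stronger readings are not supported:

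- **That everyone is unblinded from week 16.** Only the last participant is; no visit through week 16 is affected by the study-wide rule.
- **That the estimate is biased by 6.7 percentage points.** That is 1/15, the weight of any single participant. It does not show that re-attribution is likely, and the two intervals overlap almost completely.
- **That weeks 48-96 are open endpoint time.** The documents do not say whether the endpoint runs past week 48.
- **That the PD-1 secondary endpoint is biased in the same way.** The relatedness judgement plays no part in it, and nothing in the texts compared here shows measurement bias.

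**What to change.** 1. **Section 5.5.1 (and 5.8 by reference).** The investigator makes a time-stamped record of grade and causality before the code is disclosed, and likewise for all open events before the study-wide unblinding. Release needed for care is never delayed. Judgements made or revised after release are flagged as such. Report the endpoint with both the blinded and the final judgement.
2. **Sections 3.2.1 and 14.** Use one primary outcome definition and one time window. As a sensitivity analysis, report endpoint-grade events by arm regardless of attribution through week 48.
3. **Section 5.5, preferable rather than essential.** Keep the staff who grade and attribute AEs blinded to the last participant's week 48 visit, or to the end of the endpoint window if that is longer.
4. **Sections 12.1 and 12.3.2.1.** Reconcile which SAEs are reported in weeks 48-96.

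**Cost.** Wording changes and one extra record at code release; no added visits or participants. Under item 3, with the blind ending at the last week 48 visit, assessors learn the arm up to 48 - 16 = 32 weeks later. That could delay planning of the follow-on work foreseen in 1.3. With 2-year accrual the last week 48 visit falls at about week 104 + 48 = 152, within a study dated January 2018 to January 2022 (about 208 weeks), so the study is not lengthened.
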